5.2.4 Enrollment Holds

Enrollment will be held if the subject experiences a grade 3 or greater ASR as determined by the Investigator. The subject must be withdrawn from the study if they experience a grade 3 ASR. Enrollment can be re-started after agreement between the Principal Investigator, Medical Monitor, and the Sponsor.

Study enrollment will be halted in the event of a death of a subject while on the study or within a 30-day period follow study drug exposure regardless of drug relationship. In the event the enrollment is halted, a clinical review of the subject case will be made by the Principal Investigator, Medical Monitor, and the Sponsor to assess the safety of the medicinal product. If the review concludes there is no association of the death with the study drug, restarting enrollment may proceed.

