5.5.2.6 Additional treatment: Every additional 21 days ± 3 days if indicated

A maximum of 9 drug administrations will be administered on this study for all patients, except in the case of progression on study and or in the case of patients who had been on study for more than 6 months at the time of this amendment. Patients with evidence of progression and declining HAAH immune parameters within 6 months of stopping therapy have the option of resuming therapy on the study protocol.

- Immunologic blood collection pre-dose on day of drug administration every 21 days thereafter if continuing treatment.
- Symptom-directed physical examination
- Vital signs and ECG
- Eastern Cooperative Oncology Group (ECOG) performance score
- Prostate-specific antigen (PSA) assessment
- Biochemical testing: chemistry, hematology, coagulation, CH50
- Study treatment administration
- Physician administration site assessment (post-administration)
- Adverse events and concomitant medications

5.5.2.7 Follow up and End of Study (EOS): 28 days \pm 3 days after last treatment for a total of 6 months

- Complete physical examination
- Vital signs
- Eastern Cooperative Oncology Group (ECOG) performance score
- ECG
- Prostate-specific antigen (PSA) assessment
- Clinical laboratory tests, chemistry, hematology, coagulation, CH50 (only on first follow up)
- Immunologic blood collection
- Adverse events and concomitant medications

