5.5.3.3 Administration site reaction

The area around the administration site will be assessed by the physician for adverse reactions at least 30 minutes post study drug administration. The Investigator will grade any ASRs according to the NCI-CTCAE V4.03 (excluding the actual expected micro-injection punctures).

Patients will be required to report any change in the administration site and return to the clinic for evaluation by the Investigator.

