7.4 Analysis of the Study

All statistical tests will be two-sided and a difference resulting in a p-value of less than or equal to 0.05 will be considered statistically significant. All p-values will be rounded to and displayed in four decimals. If a p-value less than 0.0001 occurs it will be shown in tables as <0.0001.

There will be no multiplicity adjustments.

Descriptive summaries of variables will be provided where appropriate. For continuous variables, the number of non-missing values (n) and the median, mean, standard deviation, minimum, and maximum will be tabulated by dosage group. For categorical variables, the counts and proportions of each value will be tabulated by dosage group. Since this study allows for subjects to change their dose level during additional treatment visits after Day 43, the dose level can change over the course of the study; see Section 8 for how summaries by dosage group will be handled when dose levels vary.

Expansion of descriptive table categories within each treatment may occur if such elaborations are thought to be useful.

Assessments completed during the 6-month follow up period after study treatment will not appear in any tables or graphs (unless noted otherwise), but will be included in the data listings, classified under the last dose level the subject took at the last treatment visit prior to the end of study.

All collected data will be presented in listings. Data not subject to analysis according to this plan will not appear in any tables or graphs but will be included in the data listings.

Post-hoc exploratory analyses not identified in this SAP may be performed to further examine the study data. These analyses will be clearly identified as such in the final clinical study report.

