7.4.6 Data Handling

Any administration site reaction found in the AE log that is also captured on the Physician Administration Site Assessment eCRF page will not be counted as an (unsolicited) AE to avoid duplication.

Unscheduled or repeated laboratory results will not be analyzed for the summary of continuous values.

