8.6 Safety Analysis

All safety analyses will be conducted on the Safety Population.

Unless otherwise specified, subjects will be summarized through Day 43 using the assigned dose level as the dosage group. For additional treatment visits and end of treatment phase visit, subjects will be summarized by cohort and by the dose level the subject took at the visit immediately prior to the current visit—this allows for subjects who changed their dose level to be summarized at the new (elevated) dose level.

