8.6.2 Adverse Events

The number and percent of subjects with any TEAEs will be displayed by SOC and PT for each dosage group. For additional treatment visits and end of study, the level used as the dosage group will be determined by the dose level the subject took at the start of the TEAE. Within each PT, subjects will be counted only once if they had more than one event reported during the treatment period.

For MedDRA SOC, the number and percentage of subjects experiencing at least one TEAE overall and at least one TEAE for a system will be tabulated by severity grade (Grades 1-5) and dosage group. For MedDRA PT, the number and percentage of subjects reporting at least one TEAE within a PT category will be tabulated by relationship to study products and dosage group. For the calculations in these tables, each subject's TEAEs will be counted once under the maximum severity or the strongest recorded causal relationship to study product.

Summaries will be generated for all serious TEAEs and all TEAEs causing permanent dose discontinuation by SOC and PT for each dosage group.

A listing will be produced for all subjects who reported serious TEAEs. The listing will provide details of the events including severity, relationship to study product, time between onset and last study treatment administration, and a summary of the event.

All TEAEs and non-treatment emergent AEs will be listed individually by subject.

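### After Day 43 the SAP's prior-visit dose rule tabulates the site reaction to a patient's first escalated injection under the previous, lower dose

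*SAP*

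**What the plan says.** SAP 7.4 notes that the study "allows for subjects to change their dose level during additional treatment visits after Day 43". Protocol 5.1 permits patients on continuing treatment to move up to the MTD/RP2D once it is known, with at most 9 injections.

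For those visits SAP 8.6 sets a default that applies unless something else is specified. Subjects are summarised by cohort and "by the dose level the subject took at the visit immediately prior to the current visit". The reason given is that "this allows for subjects who changed their dose level to be summarized at the new (elevated) dose level".

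SAP 8.6.1 tabulates administration site reactions by dosage group, through Day 43 and separately for later treatment visits. It does not say which dose defines the group after Day 43.

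Protocol 5.5.2.6 lists the site assessment at each additional treatment visit as a post-injection procedure, and Protocol 5.5.3.3 times it "at least 30 minutes post study drug administration".

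For TEAEs at these visits, SAP 8.6.2 has its own rule: "the level used as the dosage group will be determined by the dose level the subject took at the start of the TEAE". Under SAP 7.4.6, an AE-log reaction that is also on the site-assessment page "will not be counted as an (unsolicited) AE to avoid duplication".

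**The concern.** The prior-visit rule suits a measurement taken before that day's injection, because the latest exposure is then the dose from the visit before. Immunologic blood is such a measurement. A site reaction examined after the injection is not: the relevant exposure is the dose just given. When a patient is escalated, these two doses differ at exactly one visit, and there the rule picks the wrong one.

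Incidence of administration site reactions is a named secondary endpoint, reported by dose. The error always runs one way, from the elevated dose to a lower one. The AE tables do not correct it, because the AE-log copy, which would have been booked by dose at onset, is not counted when the reaction is also on the site page.

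**Working it through.** The documents give no figure on this point, so there is nothing to reproduce. The check follows the rule visit by visit.

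**Inputs.** Injections every 21 days, at most 9 (Protocol 5.1). Injection *i* falls on Day 1 + 21(*i* − 1), so injection 3 is Day 43, injection 4 is Day 64 and injection 9 is Day 169. Dose changes occur after Day 43 (SAP 7.4), so the first escalated injection *k* lies between 4 and 9. Through Day 43 the group is the assigned dose; afterwards it is the dose at the previous visit (SAP 8.6).

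**Booked against given.** At visit *k* the dose given is the elevated one and the dose booked is that of visit *k* − 1, the lower one. At visit *k* + 1 and later the previous dose is already the elevated one, so the two agree. Misbooked assessments per escalated patient = 1. As a share of that patient's own escalated-dose assessments, if all 9 injections are given, this is 1/(9 − *k* + 1):

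| First escalated injection *k* | Day | Escalated injections | Share misbooked |
|---|---|---|---|
| 4 | 64 | 6 | 1/6 = 17% |
| 5 | 85 | 5 | 1/5 = 20% |
| 6 | 106 | 4 | 1/4 = 25% |
| 7 | 127 | 3 | 1/3 = 33% |
| 8 | 148 | 2 | 1/2 = 50% |
| 9 | 169 | 1 | 1/1 = 100% |

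**Effect on the subject-level table.** SAP 8.6.1 counts subjects with at least one reaction, by maximum severity. Let *g_i* be the grade at injection *i*, with 0 for none.

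- Elevated-dose cell: correct value max(*g_k*, …, *g_9*); value under the rule max(*g_(k+1)*, …, *g_9*). It is too low only if *g_k* exceeds every later grade booked to that dose.
- Lower-dose cell, additional treatment visits: correct value max(*g_4*, …, *g_(k−1)*); value under the rule max(*g_4*, …, *g_k*). It is too high only if *g_k* exceeds every earlier grade there. If *k* = 4, the patient should have no entry in this cell but has one.

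In the by-visit table, Table 14.3.1.2.2, the patient sits in the lower-dose row at visit *k* whatever the grade.

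**Number of patients.** Not given. Cohorts of 3 or 6 at each of the two lower doses give a ceiling of 3 + 3 = 6 to 6 + 6 = 12 if the RP2D is 3.0×10^11 particles and every such patient is still on treatment and is escalated. The dose ratio would then be 3.0×10^11 / 1.0×10^11 = 3 or 3.0×10^11 / 2.0×10^10 = 15. If the RP2D were 1.0×10^11, only the first cohort (3 to 6 patients) could move up, with a ratio of 1.0×10^11 / 2.0×10^10 = 5.

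**After the change.** If reactions are booked to the dose injected at the same visit, the number misbooked is 0 for every *k* from 4 to 9.

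**The case against.** The literal reading is hard to contest; what can be contested is how much follows from it.

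- **Dose relationship.** A reader might infer that the rule flattens or reverses the dose relationship for site reactions. The documents do not support that. The comparison through Day 43 uses assigned dose and is untouched. After Day 43 results are split by cohort as well as dose, so patients enrolled at the highest dose keep their own rows. The error moves one assessment between cells within a lower cohort.
- **Severe reactions.** Protocol 5.2.4 states: "The subject must be withdrawn from the study if they experience a grade 3 ASR". A reader might infer that a grade 3 reaction to the first escalated injection can never appear under the elevated dose. That goes too far. SAP 8.6 books the end of treatment phase visit to the dose at the visit before it, which is the elevated dose. Protocol 5.2.3 asks for end-of-study procedures, if possible, after permanent discontinuation, and the protocol synopsis lists a site assessment at end of study. Against this, Table 1 and Protocol 5.5.2.7 omit that assessment, and the title of Table 14.3.1.1.2 covers only additional treatment visits. The reaction would also have to persist until then.
- **Unit of the percentages.** The 17% to 100% are shares of one patient's assessments, not losses in reported incidence. A patient with an equal or worse reaction at a later escalated injection is still counted correctly at the elevated dose.
- **Recoverability.** Dosing and site assessments are listed (Listings 16.2.3 and 16.2.6), so the true dose can be recovered. A reaction recorded only in the AE log keeps the onset-dose rule. SAP section 5 says analyses are as treated, and the table shells, a separate document not available here, may specify the intended dose.

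All of this limits the size and stands. None of it supplies an override in the SAP text, and the as-treated statement argues for the correction.

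**Conclusion.** The point holds for site reactions at additional treatment visits. For each escalated patient, the one assessment of the first escalated injection goes under the previous, lower dose. This contradicts the rule's own stated aim and differs from the onset-dose rule for TEAEs. The subject-level incidence or maximum grade at the elevated dose is wrong only where that first reaction is not equalled or exceeded at a later visit booked to that dose. This is most likely after late escalation or early stopping.

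The shares in the table assume all nine injections are given. The number of patients affected is unknown and is at most those in the lower cohorts still on treatment. MTD and DLT determination (first cycle only), tables through Day 43, TEAE attribution, pre-dose immunology and listings are not affected. It would be wrong to read this as a fault in the prior-visit rule for all data after escalation.

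The matter should be fixed, because it mis-states a secondary safety endpoint by dose in a small trial. No primary result depends on it.

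**What to change.** Add to SAP 8.6.1: *For visits at which study treatment is given, administration site reactions are assigned to the dose administered at that visit; assessments at visits without dosing are assigned to the most recent dose received.* Apply it to Tables 14.3.1.1.2 and 14.3.1.2.2.

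Leave the SAP 8.6 default as it is for the other safety variables. Restricting it to pre-dose measurements would leave laboratory values, vital signs, ECG and ECOG without a rule at the end of treatment phase visit, where no dose is given.

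Also reconcile the synopsis with Table 1 and Protocol 5.5.2.7 on whether the site is assessed at end of study.

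The cost is one sentence and a small programming change. Dose and time of each administration are already recorded, so no new data are needed.

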8.6.1 Administration Site Reactions

Administration Site reactions include local (injection site) reactions, such as pain, tenderness, erythema/redness, and swelling. Events are collected via the Physician Administration Site Assessment eCRF page and are graded using a severity rating of 0 (none), and 1, 2, 3, 4 (mild, moderate, severe, potentially life threatening).

A summary of the number and percentage of subjects experiencing at least one administration site reaction anytime after the first study treatment administration will be tabulated by reaction type, maximum severity, and dosage group through Day 43, and separately, for additional treatment visits after Day 43. A separate summary will be tabulated for each visit that an assessment is scheduled.

8.6.2 Adverse Events

The number and percent of subjects with any TEAEs will be displayed by SOC and PT for each dosage group. For additional treatment visits and end of study, the level used as the dosage group will be determined by the dose level the subject took at the start of the TEAE. Within each PT, subjects will be counted only once if they had more than one event reported during the treatment period.

For MedDRA SOC, the number and percentage of subjects experiencing at least one TEAE overall and at least one TEAE for a system will be tabulated by severity grade (Grades 1-5) and dosage group. For MedDRA PT, the number and percentage of subjects reporting at least one TEAE within a PT category will be tabulated by relationship to study products and dosage group. For the calculations in these tables, each subject's TEAEs will be counted once under the maximum severity or the strongest recorded causal relationship to study product.

Summaries will be generated for all serious TEAEs and all TEAEs causing permanent dose discontinuation by SOC and PT for each dosage group.

A listing will be produced for all subjects who reported serious TEAEs. The listing will provide details of the events including severity, relationship to study product, time between onset and last study treatment administration, and a summary of the event.

All TEAEs and non-treatment emergent AEs will be listed individually by subject.

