Once the MTD/RP2D is determined, patients receiving ongoing treatment may be escalated to that dose for subsequent treatments and receive a maximum of 9 injections. Patients who have received more than 9 injections due to the timing of the amendment limiting therapy to 6 months (9 doses), will be stopped at their last dose received and be followed for 6 months as with other patients. These subjects will continue to be followed for safety and biochemical PSA monitoring on a monthly basis for 6 months and are eligible to resume SNS-301 in case of increases in PSA doubling to < 90 days or other evidence of disease progression and decline in immunological parameters.

Pharmacodynamic:

Exploratory pharmacodynamic (PD) analysis will be performed using dose, vaccine-specific antibody response (geometric mean titer), antigen-specific T and B cell indices, and the relative expression of HAAH in each patient's tumor. The PD will be balanced and optimized to the degree of antigen-specific immune response and minimized for the production of regulatory immune processes.

Other Safety:

Safety endpoints will be evaluated by the incidence and severity of administration site reactions, changes in biochemical safety measures, general incidence and types of AEs, serious adverse events (SAEs), and other overt toxicities.

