Dose-escalation will proceed once all patients in a cohort (unless the MTD is observed) have completed a 21-day safety evaluation following the first dose of study treatment in the cohort. Planned treatment may continue for an additional 2 extra doses of SNS-301 administered every 21 days. Additional patients will be enrolled at the highest dose level until at least 6 patients can be evaluated even if no DLTs are observed at the dose. In patients who tolerate SNS-301, additional treatment may be continued with single doses of SNS-301 at their current dose level to maintain geometric mean titer (GMT) of HAAH antibodies to no less than 4 times the baseline value for at least six months (9 injections). Treatment will be terminated with the 9th injection or will otherwise be terminated at any time upon the observance of PSA doubling < 90 days or occurrence of unacceptable toxicity as determined by the Investigator (either for that patient or in their dose cohort). After termination, patients will be followed for an additional 6 months with monthly PSA levels and imaging studies as needed.

Once the MTD/RP2D is determined, patients receiving ongoing treatment may be escalated to that dose for subsequent treatments and receive a maximum of 9 injections. Patients who have received more than 9 injections due to the timing of the amendment limiting therapy to 6 months (9 doses), will be stopped at their last dose received and be followed for 6 months as with other patients. These subjects will continue to be followed for safety and biochemical PSA monitoring on a monthly basis for 6 months and are eligible to resume SNS-301 in case of increases in PSA doubling to < 90 days or other evidence of disease progression and decline in immunological parameters.

Exploratory pharmacodynamic (PD) analysis will be performed using dose, vaccinespecific antibody response (geometric mean titer), antigen-specific T and B cell indices, and the relative expression of HAAH in each patient's tumor. The PD will be balanced and optimized to the degree of antigen-specific immune response and minimized for the production of regulatory immune processes. Safety endpoints will be evaluated by the incidence and severity of administration site reactions, changes in biochemical safety measures, general incidence and types of AEs, serious adverse events (SAEs), and other overt toxicities.

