10.1 List of Tables, Figures, and Listings

Table No.	Description of Table	Population
4.1.1	Subject Disposition	All Subjects
4.1.2.1	Demographics and Baseline Characteristics	Safety
14.1.2.2	Demographics and Baseline Characteristics	Immunologic
14.2.1.1	Study Treatment Administration Through Day 43	Safety
14.2.1.2	Study Treatment Administration by Additional Treatment Visit	Safety
14.2.2.1	Concomitant Medications Through Day 43	Safety
14.2.2.2	Concomitant Medications For Additional Treatment Visits	Safety
14.2.3.1.1	Change from Baseline in PSA by Visit Through Day 43	Safety
4.2.3.1.2	Change from Baseline in PSA by Additional Treatment Visit	Safety
14.2.3.2.1	Summary of PSA Velocity and PSA Doubling Time Through Day 43	Safety
14.2.3.2.2	Summary of PSA Velocity and PSA Doubling Time Through End of Treatment	Safety
14.2.3.2.3	Summary of PSA Velocity and PSA Doubling Time Through End of Study	Safety
14.3.1.1.1	Summary of Worst Administration Site Reactions Through Day 43 by Grade	Safety
14.3.1.1.2	Summary of Worst Administration Site Reactions For Additional Treatment Visits by Grade	Safety
14.3.1.2.1	Summary of Administration Site Reactions by Visit Through Day 43 and Grade	Safety
14.3.1.2.2	Summary of Administration Site Reactions by Additional Treatment Visit and Grade	Safety
14.3.2.1.1	Overall Summary of Adverse Events Through Day 43	Safety
14.3.2.1.2	Overall Summary of Adverse Events For Additional Treatment Visits	Safety
14.3.2.2.1	Treatment-Emergent Adverse Events (TEAE) by System Organ Class and Preferred Term Through Day 43	Safety
14.3.2.2.2	Treatment-Emergent Adverse Events (TEAE) by System Organ Class and Preferred Term For Additional Treatment Visits	Safety
14.3.2.3.1	Treatment-Emergent Adverse Events (TEAE) by System Organ Class and Severity Through Day 43	Safety
14.3.2.3.2	Treatment-Emergent Adverse Events (TEAE) by System Organ Class and Severity For Additional Treatment Visits	Safety
14.3.2.4.1	Treatment-Emergent Adverse Events (TEAE) by Preferred Term and Relationship to Study Treatment Through Day 43	Safety
4.3.2.4.2	Treatment-Emergent Adverse Events (TEAE) by Preferred Term and Relationship to Study Treatment For Additional Treatment Visits	Safety
4.3.2.5.1	Serious Treatment-Emergent Adverse Events (TEAE) by System Organ Class and Preferred Term Through Day 43	Safety
4.3.2.5.2	Serious Treatment-Emergent Adverse Events (TEAE) by System Organ Class and Preferred Term For Additional Treatment Visits	Safety

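### After Day 43 the adverse event tables give the percent of subjects by dose at onset without regard to injections received at that dose, so equal risk per injection can appear as a dose or cohort difference of either sign.

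*SAP*

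**What the plan says.** SAP 8.6.2 sets the statistic: "The number and percent of subjects with any TEAEs will be displayed by SOC and PT for each dosage group". Once a subject is past Day 43, the column is no longer fixed by the assigned dose. Instead, up to the end of the study, "the level used as the dosage group will be determined by the dose level the subject took at the start of the TEAE". A repeat of the same type of event does not add to the count: "Within each PT, subjects will be counted only once if they had more than one event reported during the treatment period". SAP 10.1 lists one pooled table of each kind for the period after Day 43 (Tables 14.3.2.1.2 to 14.3.2.6.2). Table 14.3.2.2.2, for example, is titled "Treatment-Emergent Adverse Events (TEAE) by System Organ Class and Preferred Term For Additional Treatment Visits".

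The SAP recognises that dose can vary within a subject; SAP 7.4 begins its explanation with "Since this study allows for subjects to change their dose level during additional treatment visits after Day 43". The route is in Protocol 5.1: once the MTD or RP2D is known, "patients receiving ongoing treatment may be escalated to that dose for subsequent treatments and receive a maximum of 9 injections". Treatment may also be "terminated at any time upon the observance of PSA doubling < 90 days or occurrence of unacceptable toxicity" (SAP Section 4). The same section provides for subjects who had already passed nine injections when the cap was introduced, and has cohorts enter one after another.

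Injections are summarised by dosage group under SAP 8.1 (Tables 14.2.1.1 and 14.2.1.2). Nothing in 8.6.2 or the table list links them to the adverse event percents.

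**The concern.** The chance that a subject has at least one event at a dose level grows with the number of injections received there. A subject with one additional injection at a level and a subject with six carry the same weight in a percent of subjects. When escalation falls partway through the additional treatments, the columns can therefore differ with no difference in risk per injection. SAP 8.6.2 also does not say whether a switched subject enters the denominator of one column, of both, or of a column before any injection at that level.

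Overall safety is the secondary objective, and these are the only adverse event summaries covering injections 4 onward. With 12 to 18 subjects and no planned tests, the tables will be read by comparing columns. The protocol synopsis also leaves room for safety data to move the RP2D away from the MTD.

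**Working it through.** **Figures in the documents.** The documents give neither a TEAE rate nor an expected number of injections per level. The one stated design figure, approximately 18 subjects, is 3 levels × 6. With no DLT the escalation rules give 3 + 3 + 6 = 12. The figure of 18 does not bear on this point; 12 is used below.

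**Inputs from the documents.** Injections every 21 days, at most 9, the third on Day 43, so 9 − 3 = 6 additional injections. A 21-day wait after the first subject of a cohort, and 21 days after the last before escalating. RP2D = highest dose if no MTD is observed.

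**Assumptions.** Risk p per injection is the same at every dose (0.10, with 0.05 and 0.20 as a range). Enrolment is as fast as the rules allow. Everyone below the top dose escalates at the first injection on or after the RP2D is declared. Nobody stops early or exceeds nine injections. Each column's denominator is the subjects with at least one additional injection at that level.

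**Timetable (study days from the first subject's first dose).** Low-dose starts: 1, 22, 22. Middle: 43, 64, 64. High: 85, then five at 106. The last high-dose subjects complete 21 days at 106 + 21 = 127, the earliest RP2D date. A subject's additional injections fall at start + 63, + 84, …, + 168.

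**Formula.** P(at least one event in k injections) = 1 − (1 − p)^k. At p = 0.10:

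| k | 1 | 2 | 3 | 4 | 5 | 6 |
|---|---|---|---|---|---|---|
| % | 10.0 | 19.0 | 27.1 | 34.4 | 41.0 | 46.9 |

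**RP2D declared on day 127.** Additional injections per subject are:

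- Low: 3, 2, 2 (total 7). Expected percent (27.1 + 19.0 + 19.0)/3 = 21.7%.
- Middle: 1, from one subject. 10.0%.
- High: 3, 4, 4, 5 and eight subjects with 6 (total 64). (27.1 + 2 × 34.4 + 41.0 + 8 × 46.9)/12 = 42.7% from these rounded entries, 42.6% unrounded.

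**Other dates.** Expected percent, with subjects / injections in brackets, p = 0.10:

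| RP2D declared | Low | Middle | High |
|---|---|---|---|
| Day 127 | 21.7 (3 / 7) | 10.0 (1 / 1) | 42.6 (12 / 64) |
| Day 169 | 36.6 (3 / 13) | 21.7 (3 / 7) | 35.4 (12 / 52) |
| Day 190 | 42.9 (3 / 16) | 29.5 (3 / 10) | 34.0 (11 / 46) |
| No escalation | 46.9 (3 / 18) | 46.9 (3 / 18) | 46.9 (6 / 36) |

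**Range over p.** Day 127 gives 11.3 / 5.0 / 23.8% at p = 0.05 and 40.3 / 20.0 / 68.7% at p = 0.20. Day 190 gives 23.9 / 15.7 / 18.8% and 69.4 / 52.2 / 56.0%.

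**More than nine injections.** A low-dose subject with 12 in total, all at that dose, has 9 after Day 43: 61.3%, against 46.9% for six at the top dose.

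**Splitting by cohort as well (the SAP 8.6 default), day 127.** At the RP2D, cohort 1 (k = 3, 4, 4) shows (27.1 + 34.4 + 34.4)/3 = 32.0%, cohort 2 (k = 5, 6, 6) shows (41.0 + 46.9 + 46.9)/3 = 44.9%, and cohort 3 (k = 6) shows 46.9%. The artefact moves to a cohort difference at one dose, mainly in cohort 1.

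**Per injection, day 127.** Expected events / injections are 0.7/7, 0.1/1 and 6.4/64: 0.10 in every column.

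**The case against.** The strongest case against is that little depends on these tables. Protocol 6.1 plans no formal analysis, and the MTD rests on the first 21 days. The tables through Day 43 already compare three injections at the assigned dose on a common schedule. After Day 43, site reactions, laboratory values, vital signs, ECG and ECOG score are tabulated by visit. Injections appear in Table 14.2.1.2, and Listings 16.2.3 and 16.2.7 would let a reader rebuild exposure. A three-subject column can read only 0, 33, 67 or 100%, so chance outweighs much of the artefact.

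All of that stands and limits the importance of the point. It does not remove it: the TEAE tables have no by-visit version, and a reader should not have to rebuild exposure from listings to know whether two columns are comparable.

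Three stronger readings are tempting, and the documents do not support them.

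- A reader might infer that the plan always understates the lower doses and so creates an upward dose trend. The sign depends on when the RP2D is declared: at day 169 low and high are almost level, and at day 190 low exceeds high.
- A reader might infer that these columns are the only repeated-dose safety comparison. The through-Day-43 tables are another.
- A reader might take it as stated that a switched subject counts as a whole subject in both columns. SAP 8.6.2 leaves this open, and the table shells are in a separate document.

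A per-injection rate has weaknesses too. It assumes roughly constant risk, whereas the animal antibody response depended on the number of doses (Protocol 3.2, 3.4). One subject's recurrent events could dominate a column of seven injections. Intervals may stretch to 42 days (Protocol 5.3.5.2), so injections are not the same as time.

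**Conclusion.** The concern holds as a possible distortion of the TEAE tables for additional treatment visits, with no fixed direction. Under equal 10% risk per injection, the high-minus-low gap runs from +20.9 points (42.6 − 21.7, RP2D on day 127) to −8.9 points (34.0 − 42.9, day 190), and is zero if nobody escalates or stops early and all have nine injections. These sizes rest on the assumed risk, the 12-subject timetable and universal escalation; the documents give no actual exposure, and escalation is optional. The MTD decision and the through-Day-43 tables are not touched. The change is worth making before the tables are produced, but no primary conclusion depends on it.

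**What to change.** In SAP 8.6.2, for Tables 14.3.2.1.2 to 14.3.2.6.2:

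1. Define each column's denominator as subjects with at least one additional injection at that dose level, and state that the once-per-preferred-term rule applies within a level.
2. Show in the column header the number of injections, and the time, at that level.
3. Report TEAEs per injection (or per unit of time at that level) beside the percent of subjects.
4. Add a footnote that crude percents are not comparable between levels when exposure differs.

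The cost is SAP wording, a header line and one extra column per table, from dosing data already collected. The tables become busier. Because the rate assumes roughly constant risk and is fragile in small columns, it should supplement the percent, not replace it or serve as the sole basis for comparing levels.
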